### **1.1.2.3 Pharmacokinetics (PK) and Pharmacodynamics (PD)**

PD and PK will additionally be evaluated as endpoints:

- PK parameters maximum serum concentration ( $C_{max}$ ), area under the curve (AUC), time to maximum plasma concentration ( $t_{max}$ ), terminal half-life ( $t_{1/2}$ ), V, clearance (CL), of imlifidase
- PD effect on IgG following administration of imlifidase
- PD effect on identified autoantibodies regarded as GBS disease specific following administration of imlifidase.

To note, identification of post-infusion antibodies is described in [section 1.1.2.4](#).

### **1.1.2.4 Exploratory Endpoint**

Biomarker assessment (analysis of anti-ganglioside antibodies and neurofilament light chain levels) will be evaluated as an exploratory endpoint.

## 2 Study design

The study is an open-label, single arm, multi-centre, phase II study of imlifidase in combination with standard care IVIg in subjects within 10 days of onset of GBS.

The study will recruit approximately 30 subjects (adult males or females) with GBS eligible for IVIg treatment based on current practice (i.e. GBS disability score  $\geq 3$  at time of screening for enrolment and within 10 days of onset of weakness).

Data from each subject enrolled in this study will, if feasible, be compared with an external control group consisting of matched subjects from the IGOS database (International Guillain-Barré Syndrome Outcome Study, ClinicalTrials.gov Identifier: NCT01582763). If such an indirect comparison study is feasible, details pertaining to the comparison will be outlined in a separate non-interventional study protocol. This data will be handled according to a separate SAP.

### 2.1 Overview of study procedures

All subjects will receive imlifidase (Day 1) prior to standard of care IVIg. Disability scores to assess disability status and capture activities and social participation will be evaluated. Blood samples for safety, pharmacokinetics, and pharmacodynamics will be collected, and subjects will be closely monitored after infusion with imlifidase.

Subjects will be followed clinically on days 1-8, 15, 29, 57, 92 and 180 days after imlifidase infusion and additionally with a 360-day telephone contact to assess GBS DS, R-ODS, capture health status in a questionnaire, and AEs.

Safety parameters will be measured up to Day 180. Concomitant medication will be recorded throughout the study.

Reporting of adverse events will be done from signing of informed consent and throughout the study.

After study completion, all study subjects will be followed up regularly according to clinical practice at the site in question.

Figure 1. Overview of study

The planned tests are summarised in the **Study Flow Chart Table** outlined in the study protocol.

Note, schedule of Study Flow Chart (i.e., assessments and procedures) may change between protocol versions, please refer to corresponding schedule relevant for each protocol version.

## 2.2 Determination of sample size

No formal sample size calculations have been performed for this study. Approximately 30 evaluable subjects will be enrolled and are considered sufficient to provide adequate information about the safety and efficacy.

## 2.3 Blinding

Blinding is not relevant since this is an open-label study, and all subjects will receive a dose of imlifidase, 0.25mg/kg.

## 2.4 Data pre-processing

Difference between the value at each assessment and value at baseline for the efficacy parameters as an absolute change and percentage change will be calculated as:

$$\text{Absolute change at visit } x = \text{Value at visit } x - \text{value at baseline}.$$

$$\text{Change in \% at visit } x = \frac{\text{absolute change at visit } x}{\text{value at baseline}} \cdot 100.$$

The proportion of subjects with improvement since baseline at each visit will be calculated as:

$$\text{Proportion at visit } x = \frac{\text{number of subjects with improvement at visit } x}{\text{number of subjects at baseline}}.$$

Mean difference from baseline to each visit will be calculated as:

$$\text{Mean difference at visit } x = \frac{\text{sum of absolute change from baseline at visit } x}{\text{number of subjects at visit } x}.$$

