## **11. DATA MANAGEMENT**

At clean file, data from visit 1 to 9 will be evaluated and reported in the Clinical Study Report (CSR). Data from visit 10 will be reported separately as an addendum to the CSR.

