## 14. REPORTING AND PUBLICATION

### 14.1 Clinical Study Report

The main analyses for the clinical study report (CSR) will be based on all data when all patients have had visit 9 (Day 180). Data from visit 10 (Day 360) will be reported as an addendum to the CSR. The full CSR including addendum will be available within one year after end of study (for definition see [Section 3.5](#)).

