## 1.1.2 Endpoints

### 1.1.2.1 Efficacy

The efficacy endpoints are the following:

- GBS Disability Score (DS):
  - Proportion of subjects with improvement of one or more grades in disability outcome (on the 6-point GBS DS) over time (i.e., at all post-baseline visits)
  - Proportion of subjects with improvement of two or more grades in disability outcome (on the 6-point GBS DS) over time (i.e., at all post-baseline visits)
  - Proportion of subjects with improvement of three or more grades in disability outcome (on the 6-point GBS DS) over time (i.e., at all post-baseline visits)
  - Change in GBS DS over time (i.e., at all post-baseline visits)
  - Proportion of subjects able to walk unaided ( $GBS\ DS \leq 2$ ) over time (i.e., at all post-baseline visits)
  - Time (days) to improvement by at least one, two and three grade(s) on the GBS DS
  - Time (days) to walk independently ( $GBS\ DS \leq 2$ )
  - Proportion of subjects that reach  $GBS\ DS \leq 1$  by week 26
  - Time (days) to run ( $GBS\ DS \leq 1$ )
- Rasch-built Overall Disability Scale (R-ODS):
  - Proportion of subjects with an increase from baseline in R-ODS scale by at least 6 points on the centile metric score over time (i.e., at all post-baseline visits)
  - Proportion of subjects with all R-ODS items above 0 at week 26
- Change in MRC sum score over time (i.e., at all post-baseline visits).
- Ventilation support (GBS DS 5):

- Proportion of subjects requiring mechanical ventilation support (GBS DS 5) (i.e., at all visits)
- Time (days) on mechanical ventilation
- Time (days) in hospital and in an ICU
- Quality of life as measured by EurQol EQ-5D Health Questionnaire (EQ-5D-5L) at 4 weeks and later.

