## 4.7 Efficacy analysis

### 4.7.1 GBS Disability Score (GBS DS)

The GBS Disability Score (GBS DS) used for the efficacy endpoints will be assessed for all subjects as per the schedule of assessments. The score is defined as follows:

0 = Healthy

1 = Minor symptoms and capable of running (subjects must be asked to run)

2 = Able to walk independently 10 meters or more but unable to run

3 = Able to walk more than 10 meters across an open space with help

4 = Bedridden or chair bound

5 = Needing mechanical ventilation

6 = Dead

Summary statistics will be presented in tables for the actual values and absolute change from baseline by time point. Also, shift tables will be presented to show the change from baseline as compared to post-baseline visits for the GBS DS.

In addition, the number and percentages of subjects with improvement of at least one, two or three grades, respectively, on the GBS DS will be presented by time point.

Similarly, the number and percentage of subjects able to walk unaided (GBS DS  $\leq 2$ ) and run (GBS DS  $\leq 1$ ), respectively, will be presented by time point.

Lastly, the following Kaplan-Meier analysis summary tables and plots will be presented:

- Time to improvement by at least one grade on the GBS DS
- Time to improvement by at least two grades on the GBS DS
- Time to improvement by at least three grades on the GBS DS
- Time to walk independently (GBS DS  $\leq 2$ )
- Time to run (GBS DS  $\leq 1$ )

Study end/discontinuation will be considered as censoring for subjects that do not have the event. In addition, the survival function will start at 0, since all these are “positive” events.

For each endpoint two separate Kaplan-Meier plots will be presented, one up to Day 29 (collected part of Visit 6) and one up to Day 360 (collected as part of Visit 10), including the subjects at risk at specific timepoints. Also censored observations will be marked as such on the plot.

The summary tables for the corresponding Kaplan-Meier analysis will include the following for specific timepoints up to Day 360: subjects at risk, number of subjects with events, censored observations, proportion estimates and associated pointwise 95% confidence interval (CI).

A separate table will present the number of subjects included in the analysis with corresponding number of events, number of censored observations and summary statistics for the time to event (minimum, maximum, median and associated 95% CI, quartiles).

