## 5 Interim analyses

No interim analyses are planned.

The main analyses for the CSR will be based on all data up to and including visit 9 (Day 180). To note, at time of the main analysis some subjects will have also the visit 10 (Day 360) performed, ie will have completed the study. All data available at time of database lock will be included in the main analyses, meaning that some subjects will have completed the study.

Remaining data from visit 10 (Day 360) will be included in an addendum to the CSR.

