## 6 Deviations from protocol analysis

The following changes have been considered in current SAP as compared to study protocol:

- Minor wording on the FAS definition as compared to protocol. Change has been made in order to make the definition clearer.
- Percentage change from baseline summaries will be not presented for the vital signs and laboratory assessment results (ie clinical chemistry, haematology and urinalysis).
- The main analyses for the CSR will be based on all data included in the database at time of database lock, including visit 10 (Day 360) data for subjects that reached that stage (ie completed the study).

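### In the main CSR, the Day 360 GBS DS improvement proportions count subjects whose Day 360 visit is not yet due as not improved

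*SAP*

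**What the plan says.** **The formula.** SAP 2.4 introduces it with "The proportion of subjects with improvement since baseline at each visit will be calculated as" and sets the denominator to the "number of subjects at baseline", the same at every visit. The mean difference in the same section is divided by the subjects at visit x instead.

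**Where it applies.** SAP 1.1.2.1 lists the one-, two- and three-grade GBS DS improvement proportions as endpoints at all post-baseline visits. SAP 4.7.1 says that the number and percentage with "improvement of at least one, two or three grades, respectively, on the GBS DS will be presented by time point", and states no other denominator. Protocol 6.1 (Visit 10) collects the GBS DS by telephone at Day 360.

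**Which data enter the main CSR.** Protocol 14.1 bases the main analysis on the data once all patients have had Day 180, and adds: "Data from visit 10 (Day 360) will be reported as an addendum to the CSR". Protocol 11 agrees: "Data from visit 10 will be reported separately as an addendum to the CSR". SAP 5 departs from this: "All data available at time of database lock will be included in the main analyses, meaning that some subjects will have completed the study". SAP 6 declares the change, "including visit 10 (Day 360) data for subjects that reached that stage". The remaining Day 360 data go to the addendum.

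**Missing data.** SAP 4.1.3 leaves missing values unimputed apart from listed exceptions, none of which covers the GBS DS. SAP 4.1.2 leaves the change from baseline missing when either value is missing.

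**The concern.** The baseline denominator was workable while Day 360 was to be reported only after everyone had completed. Once partial Day 360 data enter the main CSR, it treats two different groups alike: subjects who withdrew or missed the visit, and subjects for whom the visit has not come round. Counting the first group as not improved is a recognised conservative convention. Counting the second is not, because being pending says nothing about outcome; it reflects only when the subject was dosed relative to the lock.

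The study is descriptive throughout, so the printed percentages are the efficacy result. A complete Day 180 row would stand in the same table as a depressed Day 360 row, and a reader could take the shortfall for loss of improvement. Part of the figure would depend on the lock date.

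Elsewhere the SAP does protect against incompletely collected visits. SAP 4.8.2.2 and 4.8.2.3 confine vital signs and laboratory results from visits collected only up to protocol version 7.0 to listings. The Day 360 GBS DS proportions have no such safeguard.

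**Working it through.** The documents give no figure to reproduce: there is no formal sample size and no assumed response rate. The check is arithmetic on the SAP 2.4 formula.

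**1. Size of the bias.** Let N be the subjects at baseline, m those not yet due for Day 360 at the cut, and p the true proportion improved, taken as the same in pending and non-pending subjects. With no other missing data:

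- expected number improved and observed = p(N − m)
- printed proportion = p(N − m)/N
- bias = −p·m/N
- ceiling, if everyone observed improved = (N − m)/N

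**2. A range for m.** The documents do not give m. Inputs: about 30 subjects (SAP 2.2); first visit Q4 2019 and last visit Q2 2024 including 12 months of follow-up (Protocol synopsis and 3.3). Even accrual is an assumption.

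- Last dosing = last visit (1 April to 30 June 2024) minus 360 days = 7 April to 6 July 2023.
- Accrual length: shortest, 31 December 2019 to 7 April 2023 = 1193 days; longest, 1 October 2019 to 6 July 2023 = 1374 days.
- *Cut at the last subject's Day 180.* Subjects dosed in the final 360 − 180 = 180 days are pending: m = 30 × 180/1374 = 3.9 to 30 × 180/1193 = 4.5. Adding the 14-day visit window gives 194 days and m = 4.2 to 4.9. Hence 4 to 5.
- *Cut at 21 February 2024*, the date of SAP v2.0, which the change log says was updated during the main analysis. Subjects dosed after 26 February 2023 are pending, that is 40 to 130 days of accrual. With 1 October 2019 to 7 April 2023 = 1284 days and 31 December 2019 to 6 July 2023 = 1283 days, m = 30 × 40/1284 = 0.9 to 30 × 130/1283 = 3.0. Hence 1 to 3.

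**3. Printed Day 360 proportion, N = 30.** The rates p are assumptions. Stricter grade thresholds cannot have higher rates, so a low value is shown as well.

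| Pending m | Ceiling | p = 90% | p = 80% | p = 40% |
|---|---|---|---|---|
| 1 | 96.7% | 87.0% | 77.3% | 38.7% |
| 2 | 93.3% | 84.0% | 74.7% | 37.3% |
| 4 | 86.7% | 78.0% | 69.3% | 34.7% |
| 5 | 83.3% | 75.0% | 66.7% | 33.3% |

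Each pending subject costs p/30: 3.0 points at 90%, 2.7 at 80% and 1.3 at 40%.

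**4. Day 180 against Day 360.** Suppose Day 180 is complete at 24/30 = 80.0%, nobody's status changes, and 5 subjects are pending. Of the 25 assessed, 20 are improved. SAP 2.4 prints 20/30 = 66.7%, an apparent fall of 13.3 points, although 20/25 = 80.0% of those assessed are improved.

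**5. Scope.** The formula in 2.4 names improvement, so the finding is firm for the three GBS DS improvement proportions. The R-ODS 6-point responders would naturally follow the same rule, but SAP 4.7.2 states no denominator, so that extension is inferred. The Kaplan-Meier analyses do not use this formula.

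**The case against.** The effect is small and temporary: one row of one report, no hypothesis test, and replaced by the addendum. SAP 5 and 6 say openly that Day 360 is partial. Other outputs give a careful reader the means to notice. The Kaplan-Meier tables run to Day 360 with numbers at risk and censoring, the numerical GBS DS summaries show n by time point, and the disposition table counts 12-month completers. The output shells are not available and might print a separate n or a footnote. The size rests on assumed accrual and rates, and 21 February 2024 is a SAP date, not a data cut-off. Finally, the SAP prints its denominator explicitly, and a fixed denominator does not strictly impute a value.

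Most of this stands as a limit on size. The percentages above are illustrative, and the protocol's 20% unable to walk after 6 months is only a loose guide to p, since it describes a different outcome at a different time. The point about explicitness also has some force: at visits everyone has reached, the baseline denominator is usable, and what it lacks is a statement of its consequence.

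None of it removes the error. Correct figures in other tables do not correct this one, and SAP 2.4 is the only written rule for it. SAP 5 itself expects only some subjects to have completed by the lock, so m is above zero by the plan's own account and the direction of the bias is not in doubt.

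**Conclusion.** The concern holds. Followed as written, SAP 2.4 with SAP 5 and 6 understates the Day 360 GBS DS improvement proportions in the main CSR by p·m/N. The direction is certain whenever any subject is pending and the true rate is above zero. The size is not fixed by the documents. Under even accrual of 30 subjects, 1 to 5 pending subjects and true rates of 80% to 90%, the shortfall is about 3 to 15 percentage points, and it is proportionately less at lower rates. It is confined to the Day 360 row of the main CSR, and the not-yet-due part disappears with the addendum. It should be fixed because the correction is cheap and the uncorrected row invites a false reading of lost benefit.

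**What to change.** In SAP 2.4, adopt one of two rules for the Day 360 improvement proportions in the main CSR.

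- **(a) Hold them for the addendum**, as Protocol 11 and 14.1 already provide. SAP 5 and 6 then need a short exception for these outputs. The cost is that the row appears later.
- **(b) Restrict to subjects who are due.** The denominator is FAS subjects dosed at least 374 days (360 plus the 14-day window) before the data cut-off, whatever their status: assessed, missed, withdrawn or dead. The numerator is restricted to the same subjects, and that n is printed. Selecting on dosing date keeps withdrawals and deaths in, which dividing by assessed subjects would not. The cost is fewer subjects, about 25 to 29 of 30 under the assumptions above, and the proportion leaves out any result from a subject assessed at Day 360 or later but still short of 374 days at the cut-off.

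At the other visits keep the baseline denominator and add a footnote that a missing assessment counts as not improved. State whether the same rule governs the R-ODS 6-point responders. If the main CSR tables already exist, a footnote to the Day 360 row giving the number not yet due would correct the reading.

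The work is essentially one sentence in SAP 2.4 and a table footnote, plus the exception in SAP 5 and 6 under (a). No new data are needed.

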## 3 Analysis sets

### 3.1 Full analysis set

The full analysis set (FAS) consists of data from all dosed subjects having a confirmed GBS diagnosis, i.e., subjects re-evaluated and having change in diagnosis (incorrectly diagnosed with GBS at study entry) will be excluded.

The FAS will be used for presentation of efficacy endpoints.

### 3.2 PK/PD analysis set

The PK/PD analysis set (PKPDAS) comprises data from all dosed subjects, with at least one PK or PD data point available post-baseline.

The PK/PD analysis set will be used for presentation of pharmacokinetic and pharmacodynamic endpoints.

### 3.3 Safety analysis set

All treated subjects are included in the safety analysis set (SAF).

The safety analysis set will be used for presentation of safety endpoints.

## 4 Statistical analyses and presentation of data

### 4.1 General considerations

In general, FAS, PKPDAS and SAF will be used for presentation of all baseline characteristics (demographics, GBS disease information, medical history, prior and concomitant medication, and physical examination), FAS will be used for efficacy endpoints, SAF will be used for exposure and compliance and safety endpoints and PKPDAS will be used for pharmacokinetic and pharmacodynamic endpoints.

Listings to be presented for all subjects, if not otherwise specified in the corresponding TFL shell.

#### 4.1.1 Data presentation

No statistical testing will be performed. Results from analyses will be presented with estimates and 95% confidence intervals (CIs). For log-transformed analyses, the anti-log transformation will be applied before presentation.

No adjustments for multiple testing will be done, since no statistical testing will be performed.

Numerical data will be presented in summary tables by number of subjects, arithmetic mean, median, standard deviation (SD), minimum and maximum. When numerical data are recorded at different time points, absolute values at each time point and changes from baseline may be presented in the summary tables.

Categorical data will be presented by number and percent of subjects as well as number of events (where applicable).

Summaries and analysis of data will in general be presented for all subjects included in the analysis set, unless otherwise specified in the output shell.

All data will be listed by subject and time point (if applicable).

#### 4.1.2 Baseline definition

Baseline value is defined as the last non-missing assessment before the subjects start on the treatment. Change from baseline will be calculated as the difference between values for a given timepoint after baseline and baseline values (timepoint after baseline value minus baseline value). If the post-baseline value or baseline value are missing, then the change from baseline will also be missing.

#### 4.1.3 Data imputation

In general, missing data will remain as missing and the missing values will not be imputed. There are some exceptions described below.

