### 1.1 Background

#### Disease and patient population

Guillain-Barré Syndrome (GBS) is an acute, paralyzing, inflammatory peripheral disease of the peripheral nervous system usually preceded by an infection or other immune stimulation that induces an aberrant autoimmune response targeting peripheral nerves and their spinal roots. It is the most frequent cause of acute neuromuscular weakness in the Western world and can occur at any age (Willison et al. 2016). GBS is a rapidly progressive disorder often leading to a severe paresis of the arms and legs. Most GBS patients also have sensory disturbance (tingling or numbness or ataxia) and pain, and some patients have double vision or problems with swallowing. GBS may also involve the respiratory muscles, leading to intensive care unit (ICU) admission and mechanical ventilation.

After onset, GBS patients have highly varying prognoses. Despite modern care, the mortality rate is 3-5%. Two thirds of the patients have severe symptoms resulting in their inability to walk unaided (van Leeuwen et al. 2016), and 20-30% require mechanical ventilation for a period ranging from weeks to months. Progression of weakness in GBS is usually rapid and reaches a nadir within 4 weeks in the majority of patients, but many develop their maximum deficit within 2 weeks (Willison et al. 2016; van Leeuwen et al. 2016). Even with subsequent recovery from the acute condition, many patients suffer from long-term complications, leaving 20% unable to walk after 6 months.

There are two major GBS electrophysiological subtypes as determined by Nerve Conduction Studies (NCS) and Electromyography (EMG):

- Demyelinating variant, referred to as acute inflammatory demyelinating polyneuropathy (AIDP)
- Axonal variants with two major subtypes, Acute Motor Axonal Neuropathy (AMAN) and Acute Motor and Sensory Axonal Neuropathy (AMSAN)

Clinically, there are multiple GBS subtypes or variants, with the best known being the Miller Fisher Syndrome (MFS) and the pure motor form (van den Berg et al. 2014; Willison et al. 2016). In addition, GBS is highly variable with respect to disease severity, clinical course and outcome.

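### GBS DS has a grade for death, but no SAP rule carries it to visits after a death, so by-visit means would describe survivors only

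*SAP*

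**What the plan says.** Protocol 7.1.1 and SAP 4.7.1 define the same seven-level scale, 0 (healthy) to 6 (dead). SAP 4.7.1 then plans: "Summary statistics will be presented in tables for the actual values and absolute change from baseline by time point". It adds shift tables against baseline, and counts and percentages of subjects who have improved, can walk unaided (GBS DS ≤ 2) or can run (GBS DS ≤ 1), all by time point. Change in GBS DS over time is a listed efficacy endpoint (Protocol 2.2, SAP 1.1.2.1).

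On missing values, SAP 4.1.3 says: "In general, missing data will remain as missing and the missing values will not be imputed". It allows exceptions, but those it lists concern adverse event and medication dates. SAP 4.1.2 adds: "If the post-baseline value or baseline value are missing, then the change from baseline will also be missing".

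SAP 2.4 uses two denominators. The mean difference at a visit is divided by the subjects at that visit. The proportion improved is divided by the "number of subjects at baseline".

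The full analysis set (SAP 3.1) is all dosed subjects with confirmed GBS, so a death does not remove anyone from it.

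**The concern.** Death is a value on this scale, and the worst one. Once a subject has died the grade is known, but no visit takes place, so nothing is recorded unless someone enters it or a program derives it. Neither document asks for either. The rules that do exist then treat the later visits as ordinary missing data.

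At stake is what the later-visit means describe. Leaving out a grade of 6 can only lower the mean or leave it unchanged, so the summary would look better than the scale's own definition implies. The improvement proportions at the same visit would still count that subject as not improved. Two GBS DS summaries at one visit would thus rest on different populations without the tables saying so.

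**Working it through.** The plan gives no figure of its own to reproduce on this point.

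**Inputs from the documents**
- N = 30: "Approximately 30 evaluable subjects will be enrolled and are considered sufficient to provide adequate information about the safety and efficacy" (SAP 2.2).
- Background mortality: "Despite modern care, the mortality rate is 3-5" per cent (Protocol 1.1).
- Grade for death: 6.

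**Assumed, because the documents do not give it**
- m, the mean grade at a late visit in the subjects still alive: range 1 to 3.
- For mean change: baseline b in a subject who dies, and mean change s in survivors.

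**Step 1. How likely is a death?** Assume independent deaths at the background rate.
- Expected deaths: 30 × 0.03 = 0.9 to 30 × 0.05 = 1.5.
- At least one: 1 − 0.97^30 = 60%, to 1 − 0.95^30 = 79%.
- At least two: 23% to 45% (binomial).

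**Step 2. Shift in the mean grade.** With d deaths scored 6, the mean is [(30 − d)m + 6d]/30. With deaths left missing it is m. The difference is d(6 − m)/30.

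| Deaths | m = 1 | m = 2 | m = 3 |
|---|---|---|---|
| 1 | 5/30 = 0.17 | 4/30 = 0.13 | 3/30 = 0.10 |
| 2 | 10/30 = 0.33 | 8/30 = 0.27 | 6/30 = 0.20 |

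**Step 3. Shift in the mean change.** The difference is d[(6 − b) − s]/30.
- b = 4, s = −2.0: one death moves −2.00 to −1.87 (0.13); two move it to −1.73 (0.27).
- b = 4, s = −2.5: one death moves −2.50 to −2.35 (0.15); two move it to −2.20 (0.30).
- b = 5, s = −2.0: one death shifts it by (1 + 2)/30 = 0.10.

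**Step 4. Proportions.** Take 24 improved as an illustration. On the baseline denominator the result is 24/30 = 80.0% whether or not the death is scored, so the improvement endpoints do not move. The formula in SAP 2.4 is written for improvement and does not clearly extend to GBS DS ≤ 2 or ≤ 1. If those used a visit denominator, the same 24 would read 24/29 = 82.8% after one death.

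**The case against.** The strongest reply is that the SAP never says visits after a death are missing. Protocol 7.1.1 has GBS DS assessed at all visits for all subjects, and a dead subject's grade is known, so one can read the plan as expecting a 6. If sites entered 6 at each later scheduled visit, the problem would not arise. This stands as a limit: the missingness is inferred from the general rule and the absence of a death rule. It does not close the gap, because nothing instructs sites or programmers to make that entry.

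Several stronger readings are tempting and are not supported:
- **That the SAP forbids scoring deaths as 6.** Section 4.1.3 is worded as a general rule with exceptions. The SAP also has derivation rules elsewhere, for missing adverse event attributes, values below the quantification limit and negative titres. The output shells, which might add detail, are not available here.
- **That the treatment effect is biased.** This is a single-arm study without hypothesis testing. Any matched comparison belongs to a separate protocol and SAP. What shifts is a descriptive mean, not a contrast.
- **That all GBS DS results are affected.** The improvement proportions are not.
- **That the Kaplan-Meier results are part of this point.** SAP 4.7.1 says "Study end/discontinuation will be considered as censoring for subjects that do not have the event" and does not mention death. That deserves its own clarification, but it is a different mechanism.

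It is also fair that a falling n would be visible, that deaths are tabulated and listed, that the median would move little or not at all, and that survivor-only summaries with deaths reported separately are a legitimate choice. They are legitimate when declared, and this plan does not declare them.

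**Conclusion.** The point holds as an omission with a predictable consequence. Applied as written, the SAP's rules remove a subject who dies from later-visit actual values, changes and shift tables, and the means then show less disability than the scale defines.

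The size is modest: about 0.10 to 0.17 grade per death and 0.20 to 0.33 for two. This rests on 30 subjects, an assumed mean grade of 1 to 3 in the others and, for mean change, similar baselines in those who die and those who survive. The 3–5% mortality is a general GBS figure and may not apply to this selected population. If nobody dies, nothing changes. No test or improvement proportion depends on the outcome.

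**What to change.** State in SAP 4.1.3 and 4.7.1 that GBS DS is set to 6 at every scheduled visit after the date of death. Apply this to actual values, change from baseline, shift tables, and the number and percentage with GBS DS ≤ 2 or ≤ 1 by time point, so that deaths stay in the denominator. Footnote each table with the number of deaths included at that visit.

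The cost is a sentence in each section and one derivation; no new data are needed. The SAP change log shows that version 2.0 was updated during the main analysis, so the rule would come after access to data. It should be documented as a late change in the CSR or in the Day 360 addendum.

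The downside is that the mean may look slightly less favourable and combines death with disability on an ordinal scale. Survivor-only means, labelled as such, can be shown alongside.
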